9. RESEARCH METHODS

9.1. Study Design

This study will use observational data from three different countries: the UK, Spain, and Sweden. It will be a retrospective cohort (patients prescribed linaclotide) study design.

9.2. Setting

9.2.1. Study Population

The source population for the utilisation study will be:

- UK: patients registered with a GP practice participating in the CPRD
- Spain: patients registered with a GP practice participating in the SIDIAP
- Sweden: patients registered in the NPR linked to the PDR

9.2.2. Study Cohort

The study cohort will consist of new users of linaclotide (individuals newly prescribed or dispensed linaclotide) with at least 12 months of previous enrolment in the database (baseline period) before the date of first prescription or dispensation of linaclotide (index date).

9.2.2.1 Inclusion/Exclusion Criteria

Patients in the study will be required to meet the following inclusion criteria:

- The patient has at least one prescription of linaclotide in his/her medical records anytime during the study period in the UK; for Spain and Sweden, inclusion will be determined by at least one dispensation of linaclotide).
- Patient has at least 12 months of computerised records prior to the first use of linaclotide (index date).
- Patient is active (i.e., alive and permanently registered) at index date.

The following exclusion criteria will apply:

- Patient has no follow-up time (for example, transfers out or dies on the date of the first linaclotide prescription).

Additionally, in the UK two additional exclusion criteria will be applied:

- Patient who does not meet the CPRD 'acceptable' criteria (patient is permanently registered at the practice and has a valid year of birth and gender) at index date (or equivalent for other database)
- The practice's up-to-standard (UTS) date in CPRD is later than the index date (practices meeting pre-defined quality control standards for completeness, continuity, and plausibility are registered as UTS since the date those standards are met), or equivalent for other database

No additional exclusion criteria will be applied in Spain or Sweden since all records are considered of sufficient quality to conduct research studies.

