8. RESEARCH QUESTIONS AND OBJECTIVES

8.1. Research Questions

This study will address the following primary research questions:

- What are the characteristics of patients prescribed linaclotide?
- What is the extent of linaclotide off-label use with regards to its indication?

A secondary research question will be:

- What are the linaclotide prescription patterns?

All research questions will be assessed in three different countries: the UK, Spain, and Sweden.

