9.2.2.2 Time Periods and Dates

The study period is determined by the launch date of linaclotide and subsequent uptake. The study period starts on the date of linaclotide commercialisation in each of the countries: in UK in May 2013, in Spain in September 2014, and in Sweden in February 2013.

The end of the study period is defined by the last day of patient records in the available data cut, currently planned for 31 December 2017, to allow for sufficient follow-up time (long-term use) to have

the opportunity to accrue a sizable number of subjects for descriptive purposes, and for subpopulations of interest (those with potential off-label use and potential for abuse/excessive use). Please refer to the Study Size and Data Analysis sections below.

[figure not shown]
Additionally, the database's lag time (for collected data to be available in each database, estimated as up to 8 months) needs to be factored in to determine when data will be available.

Index date (or cohort entry date) will be defined as date of the first prescription (UK) or dispensation of linaclotide (Spain and Sweden). Baseline period will be the ≥ 12 -month period before index date.

The follow-up period for each study subject will be the time from the index date to the earliest of the following dates (end of follow-up date; one day is the minimum follow-up; Figure 1):

- End of the study period for follow-up
- Disenrollment from the database (date of transfer out of the practice)
- Date of last data collection
- Death
- 1.5 times the number of days of linaclotide supply after the expiry of the last linaclotide prescription during the study period (for a total of 2.5 times the last prescription duration) plus one additional day when a potential discontinuation could be assessed (please refer to section 9.3.3 Linaclotide Treatment Outcomes below)

Figure 1. Study Periods Linaclotide DUS

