 - Bacterial/viral/parasite lab information, when available (positive versus negative or no information)

For prevalence of chronic comorbidities, prior diagnoses, or history of digestive surgery at index date, the patient's entire medical history will be explored.

9.3.3. *Linaclotide Treatment Outcomes*

Secondary outcomes of this study will be linaclotide treatment patterns. The linaclotide exposure information is characterised by the linaclotide days of supply. Days of supply will be ascertained from the prescription/dispensation information recorded in the databases and the recommended dose (one capsule of linaclotide 290 µg taken once per day) and calculated by dividing the quantity prescribed/dispensed by the daily dose. Days of supply of one prescription/dispensation are expected to be around 28 days since the 28-capsule pack will be the most widely used package size. If package size is unknown, then the median duration for patients with this information will be used (and if no median can be estimated then 28 days will be used).

Linaclotide prescription patterns of interest are:

- Discontinuation of linaclotide: defined as no prescription of linaclotide in the period of 1.5 times the number of days of supply of the last linaclotide prescription following its expiry date (Sikka et al., 2005; Peterson et al., 2007): for example, for a 28-day prescription, no new prescription in the 43 days after the expiry date of the prescription supply. The date of discontinuation is the day after the date of expiry of the last linaclotide prescription. Time to discontinuation (permanently during the study period or temporarily) is the interval between the date of the first linaclotide prescription and the date of discontinuation. Discontinuation

will be reported separately for those who permanently discontinue during the study period and for those who discontinue temporarily and subsequently restart on linaclotide (see below).

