SIDIAP is a primary care database launched in 2010, following the steps of CPRD or THIN in the UK, that collects longitudinal data from EMR from 274 primary care centres in Catalonia since 2006. Catalonia is a region with a total of 5.8 million patients who represent approximately 12% of the Spanish population (4% of the Spanish population in SIDIAP-Q with higher quality indicators). Data is updated once a year and there are several scientific publications using this data source and reporting validation study results. The date of the latest available data is December 2013, and 2014 data will be made available by May–June 2015.

Data from primary and specialised care, hospital and pharmacy data are available, as well as patient characteristics such as gender and date of birth, GP-diagnosed conditions, GP prescriptions, prescription dosing and size, date of prescription and dispensation, laboratory test results, other procedures, specialist referrals and diagnosis, hospital referrals, hospital procedures, and discharge diagnosis death rate, and pregnancy information. GP diagnoses are coded following the ICD-10 codes, and hospital admissions following the ICD-9.

SIDIAP does not transfer data to private entities, but it can carry out quality investigation projects (Bolívar et al., 2012) and submit on their completion the corresponding reports on results, which will be agreed upon with the funding body in the design stage of the study. It also allows the possibility to contact physicians (currently a group that includes 10% of the total) for extracting additional information on the patient through a questionnaire.

SIDIAP is considered to be an appropriate source of data for the execution of this as the vast majority of its patients have two and three or more years of follow-up and the database itself can link with the Drug Dispensation databases (and additionally with the Mortality Registry for Death Cause); both characteristics are relevant for the proposed linaclotide study. The objectives were reviewed by their research team who are confident about the utilisation study. They identified some challenges for the safety study, and recommended performing a preliminary descriptive and exploratory study to confirm feasibility of conducting the study and to improve the validity of the actual study results.

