Some of the challenges mentioned for the safety study were that the exact date of the prescription is only available for the first prescription. For subsequent prescriptions, only the month when it was dispensed by the pharmacy will be available. Identification of complication outcomes based on codes might be incomplete due to inconsistent recording and could be difficult to relate an episode of diarrhoea to potential complications. However, these challenges could be overcome by the use of questionnaires to a sample of physicians or the use of free text in the medical records of patients.

Alternative Candidate: Instituto Aragonés de Ciencias de la Salud (IACS)

The Public Health and Health Services Research at the IACS in the Spanish region of Aragón, has the possibility to link different electronic medical and administrative databases in the region for research purposes. With data covering 126,838 patients from six urban health centres in one Health Sector of Zaragoza, IACS covers a small percentage of the Spanish population (0.27%). When linked, these different databases provide administrative and clinical information from outpatient clinics (primary care health centres), administrative and clinical information from specialty clinics, emergency room diagnoses and care, hospital procedures and discharge diagnoses, and pharmacy prescription data.

However, the IACS does not maintain any database and, currently, each of the linkable databases belongs to two different governmental organisations which collect the data, either the Servicio Aragonés de Salud or the Departamento de Sanidad Bienestar Social y Familia. To gain access to these data, it is required to apply to each of the data custodians by presenting a research protocol with the post-authorisation approval. Then an extraction of data would be performed, tailored for each particular study. Managing a study of this kind will require, the participation of one of their researchers as principal investigator, who will be responsible for the good use of the *ad hoc* database created. Information on GP-diagnosed conditions uses the International Classification of Primary Care coding and on GP prescriptions the ATC classification codes.

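### UK patients enter on an issued prescription and Spanish and Swedish patients on a dispensation, so a never-filled UK prescription counts as 28 days of treatment then discontinuation; section 9.9 does not say so, and SIDIAP could measure it

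*Protocol*

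**What the plan says.** Section 9.2.2.1 sets two entry rules. For the UK: "The patient has at least one prescription of linaclotide in his/her medical records anytime during the study period in the UK". Otherwise, "for Spain and Sweden, inclusion will be determined by at least one dispensation of linaclotide". Section 9.2.2.2 sets time zero in the same way, as the "date of the first prescription (UK) or dispensation of linaclotide (Spain and Sweden"). Section 9.2.2 calls all of these patients new users, and the second inclusion criterion in 9.2.2.1 equates the index date with first use.

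Section 9.3.3 builds exposure from days of supply: "Days of supply of one prescription/dispensation are expected to be around 28 days". Discontinuation is dated to the day after the last supply expires, once a gap of 1.5 times that supply has passed with no renewal. Nothing requires evidence that a UK prescription was filled.

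The first primary research question in section 8.1 is "What are the characteristics of patients prescribed linaclotide". Annex 3.B describes SIDIAP as holding "GP prescriptions, prescription dosing and size, date of prescription and dispensation", but adds that "the exact date of the prescription is only available for the first prescription". After that, only the month of dispensing is known. Section 9.9 repeats the date limit. It does not mention unfilled prescriptions or the difference in entry rule.

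**The concern.** Two patients with the same history are handled differently according to country. Each is prescribed linaclotide once and never collects it. In the UK the patient is in the cohort, is credited with a full pack and is recorded as stopping. In Spain or Sweden the patient is absent.

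If discontinuation is read as stopping treatment, the error runs one way: UK early discontinuation is too high and UK duration too short. Both are operational objectives in section 8.2. A reader who sets the three countries' results side by side would take part of any UK excess in early stopping as patient behaviour, when it comes from the entry rule.

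There is also a mismatch with the primary question, which concerns patients prescribed the drug. The Spanish cohort leaves out those prescribed but not supplied, although the Spanish source is described as able to show them.

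**Working it through.** **1. Timing under the protocol's own rules** (section 9.3.3; index date = day 1; one 28-capsule pack at one capsule a day).
- Supply covers days 1 to 28, so the discontinuation date is day 29.
- The no-renewal window is 1.5 × 28 + 1 = 43 days, which reproduces the protocol's example.
- Discontinuation can be assessed on day 28 + 43 = 71, which agrees with 2.5 × 28 + 1 = 71.

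A never-filled UK prescription that is not re-issued therefore yields 28 days of treatment and an event at day 29. If a laxative, antispasmodic, prokinetic or antidepressant was started in that window and continued, the event is a switch instead. Another pack size moves the day.

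**2. Inputs for size.**
- Share of true users stopping after one pack: 1/3 (section 9.5).
- Expected days of use per year in the three equal groups: 28, 150 and 220 (section 9.5). Their mean is 398/3 = 132.7, close to the 135 stated there.
- Projected UK patients to the end of 2016: 2,674 (section 9.5, Table 3).
- Share of UK first prescriptions never filled, u: not in the protocol. Assumed at 5%, 10% and 15%, with no second prescription issued to these patients.

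**3. Formulas.**
- Apparent UK stopping at day 29 = u + (1 − u)/3
- Share of those stoppers who never took the drug = u ÷ [u + (1 − u)/3]
- Apparent mean days of use per year = 28u + (1 − u) × 132.7

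| Assumed u | Never-filled among 2,674 | Apparent stopping at day 29 | Of these, never took it | Apparent mean days per year |
|---|---|---|---|---|
| 0% | 0 | 33.3% | 0% | 132.7 |
| 5% | 134 | 0.050 + 0.317 = 36.7% | 13.6% | 127.4 |
| 10% | 267 | 0.100 + 0.300 = 40.0% | 25.0% | 122.2 |
| 15% | 401 | 0.150 + 0.283 = 43.3% | 34.6% | 117.0 |

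**4. Reversing it.** Given a value for u, the stopping share among patients who filled is (observed − u)/(1 − u). At u = 10% this is (0.400 − 0.100)/0.900 = 33.3%. For mean days it is (122.2 − 2.8)/0.9 = 132.7. One external value of u is enough for a sensitivity analysis.

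**5. What SIDIAP can supply.** Section 4.7 and Annex 3.B give it GP prescriptions, the date of the first prescription and dispensations, with linkage to dispensing data. That is enough to count first linaclotide prescriptions with no dispensation. It is not enough to rebuild the UK persistence measure, which needs the dates of later prescriptions. Section 9.9 and Annex 3.B say those are not available.

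**The case against.** The strongest reply is that the UK rule is forced by the source, since CPRD records prescriptions issued, and that the difference is stated openly in the cohort definition. That is right. The choice of source is not the fault; leaving the consequence out of 9.9 and unmeasured is.

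A second reply is that the protocol often words discontinuation as an absence of prescribing, and that an unfilled off-label prescription is still off-label prescribing. For the primary question this stands: the UK definition is the one that matches it. For duration of treatment, and for counting patients as users, it does not, because no treatment took place.

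Third, a separate analysis plan is listed in Annex 1 and may contain a sensitivity analysis. That may be so, but entry rules and limitations are set in the protocol.

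A reader might go further in three ways that the document does not support.
- Turning the day-29 figures into a UK versus dispensing-country hazard ratio and comparing it with the 1.2 in section 9.5. Section 9.7 analyses each country separately, no between-country hazard ratio is specified, and the 1.2 concerns patient characteristics.
- Citing the pooling in section 4.9 as distorting persistence. That pooling covers only the primary objectives, which are descriptive; prescription patterns are secondary.
- Supposing that Spain can be fully rebuilt on the UK definition. Only cohort entry can. Follow-up would still rest on approximate dispensing dates.

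**Conclusion.** The point holds as a bias in the UK results and an unlisted limitation. Followed as written, the plan overstates UK early discontinuation and understates UK time on treatment, and UK persistence results are not like for like with the Spanish and Swedish ones.

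The size cannot be established from the protocol. For an assumed 5% to 15% never filled, apparent day-29 stopping rises by 3.3 to 10.0 percentage points above 33.3%, and apparent mean use falls by about 5 to 16 days a year from 132.7. These figures also assume 28-capsule packs, no re-issue to patients who did not fill, all such patients counted as discontinued rather than switched, and the protocol's own one-third stopping after one pack. The direction does not depend on the chosen rate; whether the effect is material does.

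**What to change.** 1. Have SIDIAP also identify patients by first GP linaclotide prescription and report the share with no dispensation. Describe baseline characteristics and off-label use for this prescribed cohort beside the dispensed cohort.
2. Use that share, with a range around it, in a UK sensitivity analysis of discontinuation and duration among patients with a single prescription.
3. State in section 9.9 that entry and time zero rest on prescriptions in the UK and dispensations in Spain and Sweden, and give the direction of the bias in the UK results.
4. Do not present a prescription-based Spanish persistence curve as the counterpart of the UK one.

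The cost is one extra SIDIAP extraction, one UK table and a short addition to 9.9. SIDIAP already manages the Spanish data (section 9.6) and carries out projects itself (Annex 3.B), so no data transfer is needed. The downside is that the Spanish share may not transfer to the UK, which is why it should be used with a range and not as a point correction.

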9.3.4. IBS Diagnosis and Severity Definition

The target indication of linaclotide is the treatment of moderate to severe IBS-C in adults. There are several Read, ICD-9 or ICD-10 codes related to IBS, but none are specific to IBS-C. In order to identify potential cases of IBS-C patients using codes, a combination of an IBS code with a code for constipation will be used. Table 4, Table 5 and Table 6 in Annex 3 include a broad list of Read codes, ICD-10 and ICD-9 codes for the identification of patients with IBS with different level of specificity, and codes for constipation to be used in combination.

There are no Read, ICD-9, or ICD-10 codes to indicate the severity of IBS. The most studied and most commonly used tools for measuring IBS severity involve quality-of-life and patient-reported symptom metrics that are not routinely recorded in the computerised databases selected for this study. Some components like symptoms or number of healthcare visits (part of the Functional Bowel Disorder Severity Index [Drossman et al., 2011]) have been previously used in the development of an IBS severity measure. However, it is not envisaged that this will be done as part of this study.

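### The UK practice-quality rule is tested only at the index date, so a patient's 12-month baseline can predate the practice's up-to-standard date

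*Protocol*

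**What the plan says.** Section 9.2.2.1 of the protocol sets two conditions that bear on the UK baseline.

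- **Length of record (all countries):** "Patient has at least 12 months of computerised records prior to the first use of linaclotide (index date"). The criterion asks for the duration of records and nothing more.
- **Practice quality (UK only):** a patient is excluded if the practice's "up-to-standard (UTS) date in CPRD is later than the index date". The same bullet explains what UTS status means: "practices meeting pre-defined quality control standards for completeness, continuity, and plausibility are registered as UTS since the date those standards are met".

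The other UK criterion, CPRD acceptability, is also assessed at the index date. It concerns permanent registration and a valid year of birth and gender, not how completely earlier events were recorded.

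Section 9.3.2 takes baseline characteristics from the period before index. For chronic comorbidities, prior diagnoses and digestive surgery it goes further: "the patient's entire medical history will be explored". Section 9.3.4 identifies IBS-C from two kinds of record: "a combination of an IBS code with a code for constipation will be used".

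**The concern.** The quality date and the look-back are each checked against the index date but never against each other. The UTS rule guarantees quality from the UTS date onward. The baseline lies before index. If the UTS date falls close to index, the guarantee covers follow-up but not the period from which the primary results are drawn.

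What is at stake is the description of patients at first prescription and the extent of off-label use, the two primary questions in section 8.1. An unrecorded diagnosis or prescription does not show up as missing. It reads as absence of the condition or drug, so the count of missing data promised in section 9.7.1 would not reveal it.

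**Working it through.** **1. The two rules on a calendar.** Let the practice reach UTS status k months before a patient's index date, with 0 ≤ k ≤ 12, and let the patient have 12 months of computerised records. Both rules admit the patient for every such k. The part of the 12-month baseline before UTS is (12 − k)/12:

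| UTS date relative to index | Admitted? | Baseline year before UTS |
|---|---|---|
| 12 months before | yes | 0/12 = 0% |
| 6 months before | yes | 6/12 = 50% |
| 1 month before | yes | 11/12 = 92% |
| on the index date | yes | 12/12 = 100% |
| after index | no | – |

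Nothing else in the protocol links the UTS date to the baseline period.

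**2. Who can be affected.** UK commercialisation began in May 2013 (section 9.2.2.2), so no index date is earlier. A practice that was UTS before May 2012 cannot produce an affected patient. Exposure is confined to practices reaching UTS from May 2012 on, and within them to patients whose index date falls less than 12 months after the UTS date.

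**3. Which variables suffer.** Co-medication comes from the baseline period and is not among the items for which section 9.3.2 searches the whole record, so it is the most exposed. Diagnoses and comorbidities are less exposed, since one code anywhere in the history is enough. For a recently qualified practice, though, the older records also predate UTS and carry no quality condition.

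**4. Direction.** IBS-C needs both an IBS element and a constipation code.

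- If the constipation code is lost, the Read-code rules in Annex 3 put a patient with IBS alone in IBS-M.
- If the IBS code is lost, the patient has constipation codes only, a group that section 9.7.1 lists under potential abuse or excessive use.

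Either loss moves a true IBS-C patient away from the licensed indication.

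**5. Size, by assumption only.** The protocol gives neither the share affected nor the loss of codes. Let p be the true IBS-C share of UK users, f the share with a pre-UTS baseline, and s the chance that an affected IBS-C patient still has both codes somewhere in the record. Then

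apparent non-IBS-C share = (1 − p) + p·f·(1 − s).

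With p = 0.7 (true non-IBS-C share 30%):

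| f | s = 0.8 | s = 0.5 |
|---|---|---|
| 2% | 30.3% | 30.7% |
| 10% | 31.4% | 33.5% |
| 20% | 32.8% | 37.0% |

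With p = 0.5 (true share 50%), f from 2% to 20% gives 50.2% to 52.0% at s = 0.8 and 50.5% to 55.0% at s = 0.5. All values of p, f and s are illustrative. The whole-history search argues for higher s, and the restriction in step 2 for lower f.

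**6. What a tighter rule costs.** The plan's own figure comes first. Section 9.5 states about 8,800 patients for a hazard ratio of 1.2, with 10% prevalence of the characteristic, 40% event probability, 90% power and two-sided 5% alpha. By Schoenfeld's formula,

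events = (1.960 + 1.282)² / [0.1 × 0.9 × (ln 1.2)²] = 3,513; patients = 3,513 / 0.40 = 8,783.

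The 8,800 is reproduced. Table 3 projects 2,674 + 2,407 + 4,584 = 9,665 patients by the end of 2016. Removing a share f of the UK users gives:

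| f (assumed) | UK patients lost | Combined total | Power for HR 1.2 |
|---|---|---|---|
| 2% | 53 | 9,612 | 92.4% |
| 5% | 134 | 9,531 | 92.2% |
| 10% | 267 | 9,398 | 91.8% |

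These are the projected numbers. Section 9.5 says the 2016 counts fell below target, so the actual totals will differ.

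**The case against.** The strongest reply is that the effect is too small to matter. Annex 3 describes CPRD as having about 10 years of follow-up on average, so practices qualifying shortly before a 2013–2017 index date are plausibly few. To appear without IBS, a patient must lack the code in the whole record, not just in the baseline year. Section 9.9 already concedes that validity depends on the quality and completeness of recording and expects some misclassification of IBS type. All of this stands and limits the size. It does not close the gap, because acknowledging a limitation is not a rule, and the whole-history search does not cover co-medication.

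Three stronger readings are tempting, and the documents do not support them.

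- **Spain.** A reader might set "No additional exclusion criteria will be applied in Spain or Sweden since all records are considered of sufficient quality to conduct research studies" against "4% of the Spanish population in SIDIAP-Q with higher quality indicators" in Annex 3 and infer a contradiction. Higher is a comparative. Annex 3 does not say that SIDIAP records outside SIDIAP-Q are inadequate, and it cites published validation work and a research team confident about the utilisation study. Splitting the projected Spanish users by subset would measure no harm.
- **A promised equivalent.** Both UK criteria mention an equivalent for another database. A reader might take this as a Spanish or Swedish rule that the next sentence withdraws. The phrase sits inside the UK-only bullets and reads naturally as another UK source. Table 7 lists THIN as the UK alternative.
- **New use.** A reader might infer that the new-user condition fails. Use before launch is impossible, and an earlier recorded prescription would itself become the index date, at which the existing UTS rule would then apply. Only wholly unrecorded prescriptions escape.

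**Conclusion.** The point holds for the UK and only there. As written, section 9.2.2.1 admits patients whose baseline year lies wholly or partly before the practice met the quality standards. The expected effect is under-recorded co-medication and, less so, under-recorded IBS, constipation and comorbidity codes, tilting classification towards apparent non-IBS-C or off-label use.

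The size is unknown from the protocol and probably small. On the assumptions in the working, an affected share of 2% to 10% adds about 0.3 to 3.5 percentage points to a true UK non-IBS-C share of 30%. The direction assumes that recording before UTS is less complete than after it, as the protocol's own definition of UTS implies. This is a cheap improvement to the eligibility wording and does not put the study's conclusions in doubt.

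**What to change.** In section 9.2.2.1, replace the UK UTS exclusion with a requirement that at least 12 months lie between the later of the patient's registration date and the practice UTS date, and the index date. The whole-history search for prior diagnoses can stay as it is.

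The cost is one wording change, one filter in the UK extraction, and the loss of a few patients from recently qualified practices. Report the number excluded by this rule, since the protocol does not give it. Spain needs no change on this point; a table stratified by SIDIAP-Q membership would be at most an optional sensitivity analysis.
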